Usability of the MeTime MS Acupressure mobile application in adults with MS

NCT07123272

Date of IRB Approval: August 22, 2025

STUDY PROTOCOL

Usability of the MeTime MS Acupressure mobile application in adults with MS

HUM00268311

Principal Investigator: [name]

BACKGROUND AND SPECIFIC AIM

Background: Multiple sclerosis (MS) is an autoimmune disease of the central nervous system that affects approximately one million people in the United States and is the leading cause of non-traumatic disability in young adults¹⁻⁴.

Fatigue is the most common symptom experienced by patients with multiple sclerosis (MS)⁵⁻⁷. The majority of persons with MS describe fatigue as their most disabling symptom, surpassing pain and even physical impairment. Fatigue impacts activities of daily living, social interactions, and quality of life, and has profound socioeconomic consequences, including loss of occupation^{6, 8-13}. Even patients who outwardly appear unaffected by MS may experience severe fatigue that causes significant functional impairment. Fatigue also remains one of the most difficult symptoms to manage, and a critical need exists to find effective alternatives for managing fatigue in MS.

Chronic pain is one of the most common and disabling symptoms in MS¹⁴⁻²⁵. Unfortunately, current pain treatments do not provide sufficient or durable pain relief^{26, 27}. Given the lack of effectiveness of conventional treatments for chronic pain, there is a dire need for effective alternatives.

Acupuncture is a component of Traditional Chinese Medicine (TCM) where thin needles are inserted at specific points on the body (*acupoints*) to treat disease and alleviate symptoms. Research over the past three decades has shown that acupuncture is effective for the treatment of chronic pain²⁸. Acupressure is a related TCM technique wherein pressure is applied with a finger or device to specific *acupoints*. Acupressure is highly scalable and can be taught to patients for self-administration. Research on self-administered acupressure is in its infancy, though promising initial data indicates that self-acupressure is effective for chronic pain^{29, 30} and fatigue³¹, with one study suggesting that self-acupressure is effective in reducing fatigue in MS³². Research has found significant improvements in pain, fatigue, sleep, and depression in breast cancer survivors^{33, 34} and improvements in pain intensity in chronic low back pain with self-acupressure³⁵. Although there is evidence that acupuncture is effective at alleviating fatigue and pain in MS³⁶, well-designed studies of self-acupressure for fatigue and pain in MS are needed to better understand the use of this therapy as complementary and integrative treatment for symptom management.

[name] adapted the existing MeTime mobile application for self-administered acupressure developed by [name] and [name]. The MeTime Acupressure app was originally developed in association with patient focus groups consisting of cancer survivors and the University of Michigan 3D Media Laboratory. The adapted app, MeTime MS, has been tailored to be more relevant to the MS population, including an updated MS-specific introduction video. Before conducting a trial of self-acupressure for pain and fatigue in adults with MS, we aim to first conduct a usability study of the adapted MeTime MS app in a small sample of adults with MS.

Specific Aim: Assess the usability of the MeTime MS mobile application in adults with MS.

METHODS

Study Sample : We will enroll 10 adults with clinically significant pain and fatigue and MS to use the MeTime MS app for 6 weeks and then participate in a focus group or one-one interview to

assess their experience with using the app. Participants in the study must be diagnosed as having MS by a physician; this diagnosis status will be confirmed through medical record review.

Inclusion and exclusion criteria :

Inclusion Criteria

- MS diagnosis (all MS subtypes included)
- Age 18 years or older
- Average Fatigue Severity Scale (FSS) score ≥ 4 at screening coupled with the opinion of the volunteer that the fatigue has interfered with their daily activities for ≥ 3 months
- Presence of chronic pain defined as moderate to severe pain for ≥ 3 -month duration that is ≥ 4 on average using a 0-10 numerical rating scale
- Home access to internet via Wi-Fi or cellular data
- Active email account

Exclusion Criteria

- Not fluent in English
- Pregnancy or breast feeding, or anticipate pregnancy in next 6 months
- Inability to use smartphone/tablet and/or MeTime MS mobile app
- Anything at the discretion of the PI or study team that would preclude participation in the study

Participant Recruitment: Participants will be recruited through existing participant registries, including the [name] Lab registry (HUM00074021), through the University of Michigan Health System clinic-based referrals, in-person recruitment, electronic medical record reviews, through local support groups and informational groups and national and regional chapters of organizations, such as the National Multiple Sclerosis Society. Flyers may be disseminated in community settings and will be advertised on the www.UMHealthResearch.org website.

Study procedures: After obtaining informed consent, participants will be assigned to use one of two versions of the MeTime MS app (N=5 each in the relaxation and stimulating protocols) for 6 weeks. Participants will be provided with their version-specific access code and may use their own smartphones/tablets or receive a loaner device from the study team. Participants will be given a large pencil with eraser or similar tool for stimulating acupressure points; participants may also elect to simply use their fingers/thumb to stimulate acupressure points.

Baseline visits will be scheduled for after the participant receives the study equipment.

The baseline visit will occur online via Zoom (or similar secure Michigan Medicine supported video conferencing system), with the following assessments and procedures completed:

- 1) Demographic Information (See table 1)
- 2) Pain and fatigue medication review (See table 1)
- 3) Brief online questionnaire via REDCap to characterize the sample (See table 1)
- 4) Orientation and training about acupressure intervention:
 - a. Orientation of MeTime-MS mobile application;
 - b. Demonstration of the location of all acupoints;

- c. Demonstration of the appropriate amount of pressure to apply to the acupoints and the correct stimulating motion.

Participants will be instructed to begin use of the app the day after the baseline visit.

The study team will contact participants weekly to assess for AEs and remain available for participant questions, concerns, and/or issues.

At the end of the 6-week period, participants will complete a usability measure (adapted System Usability Scale) and participate in a focus group or one-on-one interview. In the focus group/interview, participants will be asked about their experience using the MeTime MS app (e.g. ease of use, relevance to MS, etc.)

Participant compensation: Participants will be compensated \$25 for the baseline visit and \$75 for the focus group/interview.

Primary outcome: The focus groups/interviews will be used to gather MeTime MS app usability data. If the qualitative information collected indicates the need for substantial change to the app, then a second round of focus groups/interviews will be conducted for the original end users to provide feedback on the updated apps. User feedback will inform improvement to the app and the design of a future clinical trial.

Secondary outcome: The System Usability Scale (SUS)⁴⁰ adapted for the MeTime MS app will be used to compliment the primary qualitative data on participant perceptions of the app usability. The SUS has 10 items; the total score ranges from 0-40, with higher scores indicating better usability.

Quantitative analyses, including means, standard deviations, and percentages of the demographics and survey data will be conducted to describe the study sample.

Table 1: Study Measures	
Domain	Measure
Sample Descriptive Measures	
Demographics	Age, race, ethnicity, sex, gender, education level, etc.
Disability Level	Patient Determined Disease Steps (PDDS) ³⁷
Fatigue	PROMIS Fatigue Short Form 7a ³⁸
Pain	PROMIS Pain Intensity 3a ³⁹
Medications	Medications for pain and/or fatigue
Secondary Outcome Measure	
Usability	System Usability Scale (SUS) ⁴⁰ adapted for the MeTime MS app

Data storage: This study will use REDCap, a secure, password protected, and HIPAA compliant web-based data platform hosted by the Michigan Institute for Clinical and Health Research (MICHR) at the UM for data capture and storage. This protected database will be accessed and maintained by study personnel only. This system features both a local and remote web-based interface, secure data transfer, and an Oracle database. Data security, patient privacy, and HIPAA

requirements are a premium consideration for clinical trials research using REDCap. A complete time-stamped audit of all REDCap activity (including which and when study personnel access data) is maintained, adding to the security and fidelity of the data. Study personnel can enter data into the database through administrative access to add to the self-report data provided by participants. For self-report data collection, participants will access individualized study URLs to securely enter data on an internet-connected device of their choosing (for home-based assessments). The study URLs and REDCap surveys are separate from the acupressure app.

ADVERSE EVENT ASSESSMENTS

Adverse events reported by participants that are 1) NOT related to the normal course or chronic symptoms of MS (such as relapses, MRI progression, somatic pain, weakness, numbness, visual disturbances, bladder/bowel symptoms), and 2) NOT events that are expected to occur in the course of daily life or use of disease modifying therapy (injuries, infections, disease modifying therapy infusion reactions, disease modifying therapy injection site reactions, disease modifying therapy-induced lymphopenia).

SAE events will be collected regardless of relatedness to MS or disease modifying therapy use.

AE/SAE Reporting:

Multiple sclerosis is a disease with many disease-related symptoms and complications, and there are many common mild side effects associated with disease modifying therapy use. Due to the patient population and the nature of the disease, as well as the lack of experimental interventions in this study (only standard of care procedures and treatments will be used) we would like to implement the following AE/SAE collection/reporting guidelines:

SAE events that meet all 3 of the following criteria will be collected and submitted to the IRB within 14 days of notification (or 7 days of notification if event is fatal or life-threatening):

- Serious;
- Related (possibly, probably, or definitely); and
- Unexpected

SAEs that are unrelated, regardless of expectedness, will not be reported to the IRB.

In addition, the following AEs will be collected and submitted to the IRB:

- Any related and unexpected AE that results in a change to research or participant's treatments plan.

All other AEs documented during the study will be reported with scheduled continuation review.

SAE Definition:

An adverse event (AE) is any condition which appears or worsens after a participant is enrolled in an investigational study. An AE does not necessarily have a causal relationship with the study agent.

A serious adverse event (SAE) is an adverse experience to acupressure treatment occurring at any timepoint that results in any of the following outcomes:

- a) Death
- b) A life-threatening adverse treatment experience
- c) Inpatient hospitalization or prolongation of existing hospitalization
- d) A persistent or significant disability and/or incapacity
- e) A congenital anomaly or birth defect

Important medical events that may not result in death, be life-threatening, or require hospitalization may be considered a serious adverse treatment experience when, based upon appropriate medical judgement, they may jeopardize the patient or subject and may require medical or surgical intervention to prevent one of the outcomes listed in this definition. A serious adverse experience includes any experience that is fatal or immediately life-threatening, results in a persistent or significant disability/incapacity, requires or prolongs in-patient hospitalization, or is a congenital anomaly, cancer, or overdose.

Other important medical events that may not result in death, not be life-threatening, or not require hospitalization may be considered a serious adverse experience when, based upon appropriate medical judgement, the event may jeopardize the subject/patient and may require medical or surgical intervention to prevent one of the outcomes listed previously.

AE/SAE Relatedness:

Relatedness of an adverse event may be measured by the following definitions:

- a) Definitely related: clearly associated with study treatment
- b) Probably related: likely associated with study treatment
- c) Possibly related: may be associated with study treatment
- d) Unlikely to be related, or
- e) Definitely not related to the study treatment

For reporting purposes, an AE should be regarded as definitely or probably related to the regimen if the investigator believes that at least one of following criteria are met:

- a) There is a clinically plausible time sequence between onset of the AE and the administration of the study treatment.
- b) There is a biologically plausible mechanism for the study treatment causing or contributing to the AE.
- c) The AE cannot be attributed solely to concurrent/underlying illness, other drugs, or procedures.
- d) A potential alternative does not exist.

AE/SAE Expectedness:

Expected adverse events are those adverse events that are listed in the protocol or in the study informed consent document.

Unexpected adverse events are those that:

- a) Are not described in the clinical protocol as far as the study treatment is concerned
- b) Are not anticipated in the study informed consent. This includes adverse events for which the specificity or severity is not consistent with the description in the informed consent.

Unanticipated problem: Per FDA Procedural Guidance for Clinical Investigators, Sponsors, and IRBs (January 2009), a serious problem that has implications for the conduct of the study (requiring a significant and usually safety-related, change in the protocol such as revising inclusion/exclusion criteria or including a new monitoring requirement, informed consent or investigator's brochure).

Unanticipated problem Reporting: Per 21 CFR 312.66, 312.53 (c)(1)(vii), and 56.108(b)(1), should an unanticipated problem occur during the investigation, the investigator will promptly report all unanticipated problems involving risks to human subjects or others to IRBMED and FDA.

AE/SAE Severity:

The severity of an adverse event may be measured using the following definitions:

Mild: Noticeable to the subject, but does not interfere with subject's expected daily activities, and usually does not require additional therapy or intervention, treatment reduction, or discontinuation of the study.

Moderate: Interferes with the subject's expected daily activities, may require some additional therapy or intervention but does not require discontinuation of the study.

Severe: Extremely limits the subject's daily activities and may require discontinuation of study therapy, and/or additional treatment or intervention to resolve.

APPENDICES

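### A usability study of the MeTime MS app allows exclusion of people solely because they cannot use that app

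*Combined protocol and SAP*

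**What the plan says.** The protocol has one aim: "Specific Aim: Assess the usability of the MeTime MS mobile application in adults with MS". Under Study Sample it states: "We will enroll 10 adults with clinically significant pain and fatigue and MS to use the MeTime MS app for 6 weeks", after which participants are asked about their experience.

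The Exclusion Criteria include "Inability to use smartphone/tablet and/or MeTime MS mobile app". The list ends with a separate criterion that leaves further exclusions to the judgement of the investigator or study team.

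Study procedures then gives the order of events: "After obtaining informed consent, participants will be assigned to use one of two versions of the MeTime MS app", five people per version. Participants receive a version-specific access code and "may use their own smartphones/tablets or receive a loaner device from the study team". The baseline visit includes "Orientation of MeTime-MS mobile application". At 6 weeks, "participants will complete a usability measure (adapted System Usability Scale) and participate in a focus group or one-on-one interview".

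Under Primary outcome: "The focus groups/interviews will be used to gather MeTime MS app usability data". The adapted SUS is the secondary outcome, and the planned quantitative analysis is descriptive.

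**The concern.** Eligibility should not depend on the attribute that the study sets out to measure. Here inability to use the app is the extreme of poor usability, and the criterion makes it a sufficient reason for exclusion even in someone with adequate device skills. A person excluded on this ground gives neither an interview nor a SUS score.

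The effect can go only one way, because applying the clause removes the worst results and never the best. The interviews decide whether the app needs major revision, and the feedback also shapes a later trial. If a second round of interviews is held, it returns to the original users, so anyone excluded at entry would be missing there too. What is at stake is therefore a gap in formative feedback. The plan contains no test or SUS threshold that could be tipped.

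**Working it through.** **Inputs.** The criterion and the discretion criterion come from the Exclusion Criteria. The aim comes from Specific Aim, the sample size from Study Sample, and the order of events from Study procedures. The data sources come from Primary outcome and Secondary outcome.

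**Step 1: the only design figure.** Five per version in two versions gives 5 + 5 = 10, which agrees with the stated enrolment. No failure rate, power or precision calculation is given, so no other plan figure can be reproduced.

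**Step 2: what the app clause adds.** The app runs on a smartphone or tablet, so a person who cannot use a device cannot use the app either. Three cases remain:

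| Can use device | Can use app | Excluded by device clause | Excluded by app clause |
|---|---|---|---|
| Yes | Yes | No | No |
| No | No | Yes | Yes |
| Yes | No | No | Yes |

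The app clause changes the result only in the last row: people with adequate device skills for whom this app does not work. That is the group in which a failure points to the app rather than to the device.

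**Step 3: when the clause can operate.** Assignment, access code and orientation are all described after consent. No app test before consent is described, and neither is any method of judging inability to use the app. At screening, the clause could rest only on what a person reports or on evident incapacity. No withdrawal rule covers an enrolled participant who proves unable to use the app.

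**Step 4: what can still be seen.** The 6-week SUS and interview are for participants in general, with no condition that they used the app successfully. Partial difficulty, and inability that emerges after enrolment, can therefore still reach the results. The loss is confined to failure evident when eligibility is judged.

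**Step 5: whether a reader could tell.** No section provides for counting or reporting people excluded for app-related reasons.

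**Step 6: size.** Let *p* be the share of otherwise eligible, device-capable people who cannot use the app, and *e* the share of those who are identified and excluded when eligibility is judged. Among 10 such candidates, the expected number kept out is 10 × *p* × *e*. The documents give neither quantity. For assumed *p* of 0.05, 0.10 and 0.20:

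- *e* = 0 gives 0 in each case;
- *e* = 0.5 gives 0.25, 0.5 and 1.0;
- *e* = 1 gives 0.5, 1.0 and 2.0.

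These values show only the range that the assumptions allow. Step 3 suggests that *e* may be low.

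**The case against.** The strongest reply is that the clause can hardly operate. Candidates have no app access before consent, and Appendix A confirms that the app opens only the assigned protocol. Obvious incapacity at screening would mostly fall under the device half of the same criterion. Staff also contact participants weekly and are available for problems, so failure after enrolment has a route to the study team. This stands as a limit on size. It does not rescue the clause: if it never operates, nothing is lost by deleting it, and if it does operate, it works against the aim.

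A second reply is that the study concerns the experience of people who use the app for 6 weeks, so some ability to use it is a feasibility condition. That is a coherent intention, but the protocol does not state it. The device half of the criterion, the internet and email requirements and the loaner devices already address practical access without selecting on the app itself. Whether they are sufficient is a judgement; no section settles it.

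A third reply is that the discretion criterion would permit the same exclusions after deletion. This is correct, and the fix has to cover it.

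Three stronger readings are tempting, and the documents do not support them:

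- A reader might infer that none of the 10 participants could show complete app failure. Failure that emerges after enrolment can still appear at 6 weeks.
- A reader might infer that participants who fail at orientation will be removed. No text says so; the protocol is silent on what happens to them.
- A reader might want a confidence limit on the failure rate or an estimate of SUS inflation. The study does not set out to estimate a failure rate, its participants are not a random sample, and no input supports a figure for a SUS shift.

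**Conclusion.** The concern holds as a matter of eligibility logic. As written, the criterion allows exclusion on the outcome of interest, and nothing elsewhere in the protocol neutralises it. To the extent that it is applied when eligibility is judged, evident app failure is lost from both usability outcomes, and any bias favours the app. The size is unknown and possibly nil.

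Confidence is high about the meaning and direction of the clause and low about its practical effect. The conclusion rests on the literal reading of and/or and on usability outcomes coming only from participants; it does not rest on any assumed failure rate. The point should be fixed because the clause conflicts with the sole aim and is cheap to remove.

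**What to change.** 1. In the Exclusion Criteria, delete the words from and/or to the end of the criterion, so that it covers only general inability to use a smartphone or tablet, whether own or loaned.
2. In Study procedures, state that an enrolled participant who cannot use the app stays in the study for the interview and is reported as a usability finding, with reasons. This concerns data collection only and leaves decisions made for safety untouched.
3. In the analysis text, commit to logging and reporting the number of people excluded or withdrawn for app-related reasons, and those reasons, including anyone excluded under the investigator and study-team discretion criterion. Without that extension, the same people could be removed unseen after the deletion.

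Showing SUS scores from people who could not use the app apart from the rest is an optional presentation choice.

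The cost is a short amendment to one criterion and two or three added sentences, with no new visit or measure. The downside is that a few of the 10 may contribute little 6-week use data.

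### The unfinished adverse event sentence most naturally screens non-serious events without asking about acupressure, so events of mixed cause could go unrated

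*Combined protocol and SAP*

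**What the plan says.** Adverse Event Assessments opens with a sentence about adverse events reported by participants that meet two conditions. The first is that they are "NOT related to the normal course or chronic symptoms of MS (such as relapses, MRI progression, somatic pain, weakness, numbness, visual disturbances, bladder/bowel symptoms". The second is that they are "NOT events that are expected to occur in the course of daily life or use of disease modifying therapy (injuries, infections", with several reactions to disease modifying therapy also listed. The sentence then ends. The next one reads: "SAE events will be collected regardless of relatedness to MS or disease modifying therapy use".

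AE/SAE Reporting sends two groups of events to the IRB individually. One is events that are serious, related and unexpected. The other is "Any related and unexpected AE that results in a change to research" or to the participant's treatment plan. Remaining AEs go to continuing review, provided that they were documented. The section justifies these rules partly by the many symptoms of MS and partly by stating that the study contains nothing experimental, only standard care.

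AE/SAE Relatedness defines five categories, a to e. Category c is "Possibly related: may be associated with study treatment". For reporting, an event "should be regarded as definitely or probably related to the regimen if the investigator believes that at least one of following criteria are met". The four criteria include "There is a clinically plausible time sequence between onset of the AE and the administration of the study treatment" and "The AE cannot be attributed solely to concurrent/underlying illness, other drugs, or procedures".

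Under Study procedures, staff contact each participant every week to ask about AEs.

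**The concern.** A rule without a verb leaves staff to decide what it governs. If it governs collection, the question asked of a non-serious event is whether MS, daily life or disease modifying therapy explains it. Whether acupressure may have caused or worsened it is not asked at that step.

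The named exclusions overlap with effects that repeated pressure on the body might produce: somatic pain, weakness and numbness in the first condition, injuries in the second. Chronic pain of at least moderate intensity is an inclusion criterion, so worsened pain is hard to attribute in any participant. What is at stake is whether such events reach the relatedness assessment that the protocol itself sets up.

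**Working it through.** No arithmetic applies, and the plan gives no figure to reproduce. The check sets the rules side by side.

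**Step 1: what the opening sentence governs.** It has a subject and a relative clause, but nothing says that the events are collected, reported or ignored. The following sentence uses the verb *collected* and exempts serious events from any test of relatedness to MS or therapy. That exemption has a purpose only if non-serious events are subject to such a test, so collection is the most natural completion.

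**Step 2: apply that reading to each kind of event.**

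| Event | Opening sentence, read as a collection screen | AE/SAE Relatedness |
|---|---|---|
| Serious, any cause | Collected | Can be rated |
| Non-serious, clearly due to acupressure | Passes the first condition, which is a causal test against MS; the second should not catch it | Related |
| Non-serious, clearly due to MS alone | Set aside, as intended | Unlikely or definitely not related |
| Non-serious, mixed or uncertain cause | Not settled; may be set aside as MS-related or as a daily-life event | At least possibly related; may also meet the criterion on sole attribution |

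Only the last row is a problem. The opening sentence offers a yes/no judgement against MS, whereas the relatedness section grades causation and asks whether another cause is the *sole* explanation. An event that is never collected is never graded.

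**Step 3: look for a rule that rescues the last row.**

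- The rule on related, unexpected, plan-changing AEs presupposes that relatedness has already been judged. It does not reach an event that is expected or that changes no plan.
- Continuing review covers documented AEs only, so it does not help with an event set aside at a weekly contact.
- The definition of an AE covers any condition that appears or worsens after enrolment, but nothing says that it overrides the opening sentence.
- No section says that relatedness to acupressure is assessed before an event is set aside.

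**Step 4: check the stated reason for reduced collection.** The statement that only standard care is used does not fit Study procedures, which trains participants in an acupressure intervention, or AE/SAE Relatedness, which refers throughout to a study treatment. These descriptions need to be reconciled because the statement is part of the reason given for limiting AE collection.

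**The case against.** The strongest reply is that both the verb and the order of steps are supplied by the reader. The sentence might be meant to govern reporting, and words could be missing from the public copy. The first condition is itself a relatedness judgement, so staff could use the five categories when making it. New numbness confined to a pressed point is not obviously part of the normal course of MS, and soreness from a study procedure is not obviously a daily-life event. Limiting background events is deliberate and explained. No safety outcome is declared, and discomfort from pressing could surface in the closing focus group or interview.

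Much of this stands. It makes loss of events possible rather than certain and keeps the point small. It does not remove the point: an operative sentence is incomplete, and no section states the order in which the judgements are made.

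Several stronger readings are tempting, but the documents do not support them:

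- *Pain or numbness caused by acupressure is excluded.* The first condition excludes events related to MS, not every event of a named type.
- *The two sections flatly contradict each other.* The relatedness criteria apply for reporting purposes, and nothing says that a partial MS contribution fails the first condition.
- *With daily sessions, the time-sequence criterion fits almost any event.* The criterion requires a clinically plausible sequence; closeness in time to a session is not enough.
- *The standard-care statement shows that acupressure events are left out.* It is inconsistent with other sections but excludes no event by itself.
- *The design of the future trial would be compromised.* Under Primary outcome, user feedback is what informs that design; AE data are not mentioned.

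**Conclusion.** The point holds as a minor one, with moderate confidence. The opening sentence of Adverse Event Assessments is unfinished and, on its most natural reading, lets a non-serious event of mixed or uncertain cause be set aside before anyone rates its relation to acupressure.

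This rests on two assumptions: that the missing verb concerns collection, as the sentence on serious events suggests, and that staff would not apply the relatedness categories on their own initiative when judging the first condition. If either fails, the practical effect shrinks, but the sentence still needs completing.

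The size cannot be put in numbers, because the documents give neither an event rate nor a rate of attribution to MS. The effect is confined to safety and tolerability information. The qualitative primary outcome and the System Usability Scale are untouched, and collection of serious events is protected by its own sentence.

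**What to change.** Reconcile Adverse Event Assessments, AE/SAE Reporting and AE/SAE Relatedness by completing the opening sentence. Wording along these lines would do:

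> Every new or worsened event reported at a weekly contact is first rated for relatedness to acupressure (categories a to e). Events rated definitely, probably or possibly related are recorded, even if MS or daily life may have contributed. The MS, daily-life and disease modifying therapy exclusions apply only to non-serious events rated unlikely or definitely not related.

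In the same edit, bring the standard-care statement in AE/SAE Reporting into line with the descriptions of acupressure as an intervention and study treatment elsewhere.

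The change is to wording and uses contacts already planned: 10 participants × 6 weeks = 60 if everyone completes follow-up. The downside is somewhat more background MS symptoms to assess and record in 10 participants. How many more depends on how readily staff treat a single relatedness criterion as met. The deliberate limit on background events remains for those rated unlikely or not related.
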